8.8 Pregnancy

Women of childbearing potential must have a negative urine pregnancy test within 48 hours prior to starting treatment with study drug. Females of non-childbearing potential are defined as meeting at least one of the following criteria: (1) over the age of 60 years (2) amenorrheic for at least 2 years, (3) have had a hysterectomy and/or bilateral oophorectomy. All other females (including those with tubal ligation) will be considered to be of childbearing potential. At visits 2-12 urine pregnancy testing need only be performed if the subject has missed a menstrual cycle. The pregnancy must be followed up to determine outcome (including premature termination) and status of mother and child.

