5.2 Inclusion criteria

- Diagnosis of EBS
- Minimum EBDASI feet activity score of 2/10
- Healthy male or non-pregnant female
- Age ≥4 years old or older

- Ability to complete 7 study visits, each for approximately 30-60 minutes, including 3 scheduled phone calls within a 40-week period
- Anticipated life expectancy ≥ 52 weeks
- Males and females of childbearing potential should be using an effective means of contraception.
- Laboratory values within the range of normal unless the PI feels they are not clinically relevant.

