8.5 Safety Assessments

Safety and tolerability of the medication will be assessed at each visit through recording of adverse events, serious adverse events, evaluation of systemic absorption through measurement of trough sirolimus levels in serum, and additional safety laboratory tests listed below will also be performed.

Investigator assessment of local skin reaction (including increased erythema, edema, weeping/exudates, flaking/scaling/dryness, scabbing/crusting, and erosion/ulceration) will be assessed independently of other adverse effects.

Serum sirolimus levels

Trough serum sirolimus levels are a frequently run outpatient laboratory ELISA assay and will be performed at Stanford University at specific study visits from baseline.

Other Safety Laboratory Assessments

The clinical safety laboratory parameters will be assessed at each study visit. Laboratory tests may be repeated more often if clinically indicated.

All out-of-normal range laboratory values must be evaluated by the Investigator or subinvestigator as to whether they are clinically significant (i.e., require medical intervention or have clinical signs and/or symptoms). Abnormal clinical laboratory parameters that are considered clinically significant by the Investigator will be recorded on the Adverse Event (AE) Case Report Form (CRF) except Baseline visit. Clinically significant laboratory abnormalities noted from the Baseline visit will be recorded as medical history. The AE should be reported as a clinical diagnosis when possible. Laboratory tests will be performed at Stanford Children's Health clinics.

Urine Pregnancy Tests (UPT) will be performed at each scheduled visit on female subjects of childbearing potential starting at Baseline. If a UPT results in a positive test, the subject must be discontinued.

Sample management (collection, storage, shipping, etc...) will be done according to Stanford Clinical Laboratories standards and policies.

Clinical safety laboratories will include:

- Full blood count (CBC, Metabolic Panel, Liver function tests)
- Lipid panel profile
- Urinalysis
- Sirolimus trough (at specific study visits)

These will be performed at each scheduled study visit from screening/baseline visit (7 total), except for sirolimus trough.

Adverse Events (AE) and Serious Adverse Events (SAEs)

1. AE frequency, severity, and relationship to IMP.
2. Frequency of withdrawals due to treatment-related AEs.
3. Frequency of serious adverse events (SAEs)

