Defect area measurement using Visitrak	X		X	X		X		X	X	X	
2D photography of feet	X		X	X		X		X	X	X	
EBDASI feet score	X		X	X		X		X	X	X	
EBDASI total score	X			X		X			X		
QOLEB	X			X		X			X		
5-D Pruritus Scale	X			X		X			X	X	
Plantar pressure measurement	X			X		X			X	X	
Study drug collection/weighing/accountability	X		X	X		X		X	X		
Supervise study drug self-administration ¹	X		X			X		X			
Fitbit (daily)	X	X	X	X	X	X		X	X	X	X

Collection of blood for:											
Urine Pregnancy Test ^h	X		X	X		X		X	X	X	
				(EOT) ^a					(EOT) ^a		
Visit Number	1	□ ^b	2	3	□ ^b WASH-OUT	4	□ ^b	5	6	7	□ ^b
Study Week	Week 0	Week 2	Week 4	Week 12		Week 16	Week 18	Week 20	Week 28	Week 32	Week 40
Sirolimus trough level			X	X				X	X	X**	
Urinalysis	X			X		X			X	X	
CBC	X		X	X		X		X	X	X	
Metabolic panel	X		X	X		X		X	X	X	
Lipid profile	X		X	X		X		X	X	X	
Skin biopsy (optional)	X			X		X			X		
Structured phone-call		X				X		X			X

If a washout period is needed prior to baseline, subject has up to 6 weeks before starting treatment.

a. EOT= End of Treatment

b. After screening, subject will be randomized and enter Phase 1, the initial treatment application period. Subject will receive study drug or vehicle during this 12-week treatment period.

c. When Phase 1 is complete, a wash-out period will occur, which will last 4 weeks.

d. Phase 3 is the secondary treatment application period. The subject will receive either study drug or vehicle, switching from treatment initially used in Phase 1 during this secondary 12-week treatment period. Phase 3 may be delayed if subject has not reached 20% baseline EBDASI activity / Visitrak 2cm diameter.

e. Phase 4 will be a 4 week follow-up period after study treatment has concluded.

f. A scheduled phone call will occur at Week 40, after post treatment period at Phase 3.

g. Structured physician phone-call will be scheduled

h. Eligible female subjects of childbearing potential

i. Application occurs at the site on visit days

Table 3: Trial Objectives and Outcome Measures

Primary Objectives	Primary Outcomes

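### Read literally, section 8.8 lets two years of amenorrhea from any cause count as non-childbearing potential, so a fertile participant could fall outside the mandatory pregnancy tests

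*Combined protocol and SAP*

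**What the plan says.** Section 8.8 gives three routes to non-childbearing status, and any one is enough. The first two read "over the age of 60 years (2) amenorrheic for at least 2 years"; the third is surgical removal of the uterus or both ovaries. Everyone else is covered by a cautious default: "All other females (including those with tubal ligation) will be considered to be of childbearing potential".

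Four provisions depend on that class:

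- Pre-treatment test, 8.8: "Women of childbearing potential must have a negative urine pregnancy test within 48 hours prior to starting treatment with study drug".
- On-study tests, 8.5: these "will be performed at each scheduled visit on female subjects of childbearing potential", starting at Baseline.
- Table 2, footnote h to the urine pregnancy test row: "Eligible female subjects of childbearing potential".
- Contraception, 5.2: "Males and females of childbearing potential should be using an effective means of contraception".

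Section 8.8 also has its own rule for later visits: "At visits 2-12 urine pregnancy testing need only be performed if the subject has missed a menstrual cycle". On a positive result, 8.5 says: "If a UPT results in a positive test, the subject must be discontinued".

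**The concern.** Absence of bleeding is not the same as absence of fertility. Hormonal contraception, other drugs and some reversible conditions can stop bleeding for two years in a person who can still conceive. The second criterion does not separate these causes from menopause. It also sits oddly beside the default, which keeps a woman with tubal ligation in the tested group but could release a woman whose amenorrhea comes from a contraceptive she may stop.

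What is at stake is detection. The plan excludes pregnancy at entry (5.3) and stops treatment on a positive test, but a participant placed in the wrong class has no required test that could turn positive. Each participant who completes the crossover receives 12 weeks of sirolimus. Systemic uptake is something the trial sets out to measure, since trough levels are part of a primary outcome (8.3). That makes exposure in pregnancy possible; it does not show harm.

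**Working it through.** This is a check of the text plus a count of scheduled tests. The plan gives no figure of its own to reproduce.

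**Step 1: apply the definition.** Take a 30-year-old with uterus and ovaries intact and bleeding suppressed for two years or more.

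- Criterion (1), older than 60: not met.
- Criterion (2), two years without menstruation: met.
- Criterion (3), surgery: not met.

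One criterion is enough, so the literal result is non-childbearing. No other section narrows criterion (2).

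**Step 2: follow the class through.** The pre-treatment test (8.8), the scheduled tests (8.5 and Table 2, footnote h) and the contraception criterion for females (5.2) are all limited to childbearing potential. None then applies to her.

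**Step 3: count the tests.** The urine pregnancy test row of Table 2 is marked at Weeks 0, 4, 12, 16, 20, 28 and 32. That is 1 at Week 0 plus 6 later, 7 in all. Sections 8.5 and 8.8 disagree about the later tests, so the loss is worked out under each:

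| Governing text | Due if classed as of childbearing potential, while not bleeding | Due if classed under (2) | Loss caused by (2) |
|---|---|---|---|
| 8.5 and Table 2 | 1 + 6 = 7 | 0 | 7 − 0 = 7 |
| 8.8 | 1 + 0 = 1 | 0 | 1 − 0 = 1 |

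The 0 later tests in the 8.8 row arise because a participant with no expected cycle has none to miss. That is so whichever class she is in, so criterion (2) is not the cause of those 6 missing tests.

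**Step 4: look for another required test.** Good health and absence of pregnancy are entry conditions (5.2). Serious illness and pregnancy exclude (5.3), and meeting an exclusion later means withdrawal (5.4). Medication history is taken at screening (8.1), and concomitant medications are reviewed at the same 7 visits (Table 2). Each of these narrows the exposure. None requires a pregnancy test for a participant classed as non-childbearing.

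**The case against.** The best defense is that the literal reading is not the intended one. Criterion (2) stands between age above 60 and surgical removal, and the sentence after the list keeps women with tubal ligation in the tested class. That context points to lasting loss of fertility. Medically qualified investigators carry out the assessments (8.0) and would probably read it so. They may also test at their discretion. A participant suppressed by a contraceptive is protected while she uses it, and stopping it could come to light at a medication review.

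This stands as a limit on the size of the problem: the text permits the misclassification but does not show that it would happen. It does not remove the problem, because the written rule is what a site can be held to, and criterion (2) does not require her to stay on contraception.

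A reader might also infer more than the documents support:

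- *That 7 tests are lost in any event.* This holds only if 8.5 and Table 2 prevail. The conflict between 8.5 and 8.8 over later visits is a separate defect and adds no weight here.
- *That a participant whose bleeding returns stays exempt.* On a plain reading she no longer meets (2) and joins the default group. An explicit re-check would be a clarification.
- *That pre-menarchal girls, who may enter from age 4, are left untested.* Under the default they are in the tested class, and the loss is 0. Only if a site treated them as meeting (2) could tests after Week 0 be lost.

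**Conclusion.** The point holds as a narrow gap in a safety definition. As written, criterion (2) could place a fertile participant with suppressed bleeding outside every mandatory pregnancy test. The loss is 1 test per such participant if 8.8 governs and 7 if 8.5 and Table 2 govern.

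This rests on two assumptions: that a site applies the criterion literally, and that a missed cycle means the absence of an expected one. The documents give no basis for estimating how many of the 8 to 10 participants, of both sexes, would be affected; the number may be 0. It would be wrong to infer that anyone was in fact misclassed, or that the trial's results are at risk. The sample size and the primary comparison are unaffected. Severity is minor.

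**What to change.** Reword criterion (2) in 8.8 along these lines: *postmenopausal or permanent ovarian failure, with amenorrhea of at least 2 years not explained by contraception, other medication, a reversible condition or pre-menarchal age*. Permanent ovarian failure should be named, because a limit to natural menopause alone would wrongly move women with that condition into the childbearing class. The final clinical wording is for the sponsor's clinicians.

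Also state that participants of childbearing potential who do not bleed regularly have the urine test at each scheduled visit, as 8.5 and Table 2 already provide. Without this, and if 8.8 governs, the rewording restores only the pre-treatment test.

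The cost is a short text change and at most 7 urine tests per re-classed participant, all at visits already scheduled. A non-bleeding participant who was correctly classed from the start gains at most 7 − 1 = 6 tests if 8.8 governed before, and none if 8.5 did. The new wording makes explicit that pre-menarchal girls fall under the default. If the sponsor does not want young children tested, a separate line should say so and require re-classification at menarche.

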6.0 Study Design and Intervention

6.1 Study Design

This study is a prospective, double-blind, randomized, placebo-controlled crossover study at Stanford University School of Medicine, USA. It includes a 6-week screening period, followed by a 4 Phase Pilot Clinical Trial (see Table 2).

Screening: Up to 6 weeks

Phase 1: 12-week treatment period

Phase 2: 4-week wash-out period

Phase 3: 12-week treatment period

Phase 4: 4-week wash out period

Follow-up: 8 weeks after end-of-trial visit.

This research study is expected to take approximately 40 weeks. There will be 2 different parts of the study which the subject may receive for initial treatment period either (a) placebo (no drug) or (b) study drug for 12 weeks, during their enrollment in the 40-week study. After the initial 12-week period, there will be a washout period consisting of 4 weeks, before starting secondary treatment. During the secondary treatment period, a switch will occur and subject will receive either the (a) placebo (no drug) or (b) study drug depending on which treatment was received initially. At some time point during the 40-week study, at least both feet will receive study drug. There will also be a post-treatment visit at week 16 and week 32, with a post study phone call at Week 40. The end of treatment period will occur at Week 12 and Week 28, with the final in-person study visit occurring at week 32. Structured phone calls made by a physician will occur at Week 2, Week 14, Week 18, and Week 40.

The EBDASI feet score needs to be within 20% of baseline to progress to Phase 3. If subject's score does not meet this criteria the Phase 2 wash-out can be extended to 6 weeks.

Treatments are switched after Phase 2.

In-person study visits:

- Week 0 (screening/baseline)
- Week 4
- Week 12
- Week 16
- Week 20
- Week 28
- Week 32

Structured physician phone-call will be scheduled at:

- Week 2
- Week 14
- Week 18
- Week 40

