7.0 Study Treatment

7.1 Investigational Product

Topical sirolimus 2% and placebo ointment will be made and supplied by PCCA compounding pharmacy. Placebo ointment will consist of vehicle only – i.e. all the same components as the topical sirolimus 2% ointment minus the active

ingredient. Both will have the same appearance, texture and odor and will be in a matching container or tube.

Tubes will contain vehicle or sirolimus 2% ointment in a 60 gram supply, the amount of topical for twice daily application over 2 weeks. We expect 360 grams for each phase of the treatment, 720 grams total with 360 grams intervention and 360 grams vehicle. Vehicle is an ointment plasticized base contained no water that provides at least 6 months sirolimus stability (Chemistry RX, [name] April 8 communication; PCCA plasticized base information provided in Section 16). 'A kit' describes two components in a plastic bag or cardboard box: (1) vehicle (placebo) or intervention (sirolimus 2%) ointment in 60 gram tubes and (2) our "Study Drug Application Kit Instructions' (provided in Section 16).

Contents of the label will be in accordance with all applicable regulatory requirements.

Study Drug Storage: The IP will be stored at room temperature in a dry place, away from direct sunlight.

At each physician visit the participant will be re-supplied with sufficient IMP until their next visit. The containers will also be weighed to monitor how much IMP is being used.

Patients will be instructed to wear gloves and change gloves between applications.

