8.0 Study Assessments

Table 2 shows the schedule of assessments for the study. The investigators (medically qualified) are to conduct all study assessments. The investigator or designee must obtain written informed consent prior to performing any of the study information that will be recorded in source documents.

If a visit cannot be scheduled on the appropriate date, the visit should be re-scheduled as close as possible to the planned date, ideally within 3 days.

The study participants and caregivers will be given specific instructions about gentle skin care and avoid possible irritants on the treated area during the entire study. Patients will also be instructed to inspect the plantar surface daily to ensure no trauma.

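### Section 8.8 makes pregnancy tests after the first visit conditional on a missed cycle, while 8.5 and Table 2 require one at all seven visits; 8.8 needs correcting

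*Combined protocol and SAP*

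**What the plan says.** Three places in the combined protocol and SAP set the rule.

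- **Section 8.5 (Safety Assessments)** is unconditional: "Urine Pregnancy Tests (UPT) will be performed at each scheduled visit on female subjects of childbearing potential starting at Baseline". It also sets the consequence: "If a UPT results in a positive test, the subject must be discontinued".
- **Table 2 (Schedule of Events)**, in the row "Urine Pregnancy Test ^h", marks Weeks 0, 4, 12, 16, 20, 28 and 32. The footnote to that row limits it to eligible females of childbearing potential and sets no other condition. Section 8.0 gives the table its standing: "Table 2 shows the schedule of assessments for the study".
- **Section 8.8 (Pregnancy)** first sets a pre-treatment rule, "Women of childbearing potential must have a negative urine pregnancy test within 48 hours prior to starting treatment with study drug", and then relaxes testing afterwards: "At visits 2-12 urine pregnancy testing need only be performed if the subject has missed a menstrual cycle".

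Two further provisions matter for the consequence. Section 7.1 says: "At each physician visit the participant will be re-supplied with sufficient IMP until their next visit". Section 6.1 says: "The end of treatment period will occur at Week 12 and Week 28".

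**The concern.** For the same women at the same visits, 8.5 and Table 2 call for a test regardless of menstrual history, while 8.8 calls for one only after a missed cycle. The visit range in 8.8 does not fit this trial either, because 5.2, 6.1 and Table 2 all give seven in-person visits. No statement says which section governs, and 8.8, headed Pregnancy, is a natural place for staff to look.

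The rule feeds a mandatory action. Pregnancy is an exclusion criterion (5.3), meeting an exclusion criterion requires withdrawal (5.4), and a positive test requires discontinuation (8.5). These provisions work only if the pregnancy is found. Because ointment is dispensed to last until the next visit, a woman whose mid-treatment test is skipped leaves with supply for the rest of that treatment period.

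**Working it through.** **Inputs.** Visit weeks and test marks come from Table 2 and the visit list in 6.1. Dosing runs over Weeks 0-12 and Weeks 16-28 (6.1). Phone calls fall at Weeks 2, 14, 18 and 40 (6.1). Nominal weeks are used, with the standard 4-week washout.

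**Step 1: reproduce the schedule.** The marked cells in the pregnancy-test row are Weeks 0, 4, 12, 16, 20, 28 and 32. That is 7 tests at 7 visits, matching 5.2 and 6.1.

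**Step 2: compare the range in 8.8.** Visits 2 to 12 are 12 − 2 + 1 = 11 visit numbers. Visits 2-7 exist (6) and visits 8-12 do not (5).

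**Step 3: set the rules side by side.** Dosing left is the end of the treatment period minus the visit week.

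| Visit | Week | 8.5 and Table 2 | 8.8 read alone | Dosing left in that period |
|---|---|---|---|---|
| 1 | 0 | Test | Test (48-hour rule) | 12 − 0 = 12 weeks |
| 2 | 4 | Test | Only after a missed cycle | 12 − 4 = 8 weeks |
| 3 | 12 | Test | Only after a missed cycle | 12 − 12 = 0 |
| 4 | 16 | Test | Depends on whether the 48-hour rule is repeated | 28 − 16 = 12 weeks |
| 5 | 20 | Test | Only after a missed cycle | 28 − 20 = 8 weeks |
| 6 | 28 | Test | Only after a missed cycle | 28 − 28 = 0 |
| 7 | 32 | Test | Only after a missed cycle | None |

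**Step 4: find the tests that can shorten dosing under way.** Each treatment period has one test after its start and before its end: Week 4 in Phase 1 and Week 20 in Phase 3. For a sirolimus-first woman the one within active treatment is Week 4; for a placebo-first woman it is Week 20. Either way, at most 8 of the 12 sirolimus weeks remain. Tests at Weeks 12 and 28 come when dosing in that period has ended.

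**Step 5: check for a later contact.** No visit or call listed in 6.1 falls between Weeks 4 and 12 or between Weeks 20 and 28. A pregnancy missed at the mid-treatment visit therefore has no scheduled contact at which to surface before that period ends.

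**Step 6: the Week 16 test.** 8.8 ties the 48-hour test to starting study drug and does not say whether it is repeated before Phase 3. If it is, the Week 16 test stays unconditional. If it applies only at Week 0, the Week 16 test is conditional too.

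**The case against.** The strongest reply is that the documents already point to the answer. Table 2 is the named schedule, 8.5 agrees with it, and 8.8 is permissive: it says when a test may be omitted and forbids none. Testing at every visit satisfies all three places. A skipped test requires staff to prefer one sentence with impossible visit numbers over two concordant instructions. This stands, and it is why the consequence is stated only conditionally. It does not remove the conflict in the text.

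Second, the gaps in contact come from 6.1 and would remain after the fix. A test at Week 4 or Week 20 cannot detect a later conception. This also stands: only a pregnancy already detectable at that visit is at issue. Contraception is required (5.2), a test precedes treatment, and a reported missed cycle restores the test.

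Third, harm is not sized. The documents give no fetal-risk information. Section 2.2 describes systemic levels with topical use as below 2 ng/ml; Table 1 lists 5 and 8 µg/L in one series, so negligible absorption cannot simply be assumed. Neither establishes harm to a pregnancy.

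A reader might also draw two stronger inferences that the documents do not support.

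- **That a placebo-first woman loses two key tests and risks a full 12 weeks of sirolimus.** This needs the 48-hour rule to apply only at Week 0. Section 6.1 contrasts placebo with study drug, and footnotes b and d of Table 2 speak of study drug or vehicle. On that usage a placebo-first woman starts study drug at Week 16, and blinding would require the test in both sequences. The accountability row of Table 2 uses the term for both products, so the point is unsettled. The count is unstable as well: on the Week-0-only reading, Weeks 4, 12, 16 and 20 are all conditional before her sirolimus ends, which makes four rather than two.
- **That the trigger fails for women amenorrheic for less than 2 years**, whom 8.8 counts as of childbearing potential. Read literally, such a woman has missed a cycle and 8.8 would have her tested. The wording is unclear for her but does not plainly fail.

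**Conclusion.** The inconsistency is real and certain: 8.8 conflicts with 8.5 and Table 2, and its visit range does not fit a seven-visit trial. The consequence is conditional and narrow. If staff rely on 8.8, the one mid-treatment test in each treatment period depends on a missed cycle, and an already detectable pregnancy could go unnoticed for up to 8 further weeks of dosing.

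That bound assumes reliance on 8.8, conception despite contraception, a pregnancy detectable at Week 4 or Week 20, no missed cycle reported then, and dosing to the end of the period. The Week 16 test is exposed only on one reading of the 48-hour rule. The documents do not give the number of women of childbearing potential among the 8-10 planned participants, so no expected number of events can be calculated.

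This is a safety-conduct correction. It does not touch the sample size, power or the efficacy comparison, and it is not evidence that tests will in fact be missed.

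**What to change.** In 8.8, replace the sentence about visits 2-12 with: *Urine pregnancy testing is performed at visits 1-7 as specified in 8.5 and Table 2.* This also settles Week 16, since visit 4 is then tested however the 48-hour rule is read.

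The cost is one sentence in a protocol amendment. No test or visit is added, because all seven tests are already in 8.5 and Table 2. An extra test between visits after a missed cycle would be a new procedure and is not part of this correction.
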